3.3 Description of Measures

Socio-emotional development

At the 36 month time point, we will rely on the Strengths and Difficulties Questionnaire (SDQ). The SDQ is the most frequently used tool for assessing child behavior in LMIC and is highly correlated with longer scales, e.g. the Child Behavior Checklist. The SDQ is a parent report of 25 child attributes divided into five subscales: emotional symptoms, conduct problems, hyperactivity, peer problems, and prosocial behavior. We will also include an examiner report of child behavior as observed during the interview and cognitive assessment using the Behavior Observation Inventory from the Bayley Scales of Infant Development.

The Socio emotional part of Ages and Stages Questionnaire (ASQ SE) will be used to measure the socio emotional development of the child starting at 6 months of age. Interpersonal relationships, play, and leisure time and coping skills will be assessed using the Vineland Social-Emotional Early Childhood Scale. These scales are a combination of parent report and observer noted.

Cognitive development

We will use the Bayley Scales of Infant Development to measure the major areas of development including cognitive, language, motor, and adaptive functioning of the toddlers at 36 months of age. During the 6, 12, 24, and 36 month assessments we will assess child development with the Ages and Stages Questionnaire (ASQ). The ASQ is a widely used, simple set of 30 questions appropriate for 4–60-month-olds that assesses five domains of development: fine motor skills, gross motor skills, communication skills, problem-solving and personal-social skills. We will assess all five domains. Parents are asked to report age-appropriate milestones with the help of simple examiner administered examples, such as whether, at 8 months, the child plays with a toy by banging it up or down on the floor or table. The use of pictures is an especially good feature of the ASQ.

Physical development will be assessed using weight-for-age and height-for-age. Weight-for-age is sensitive to weight change over a short time period but fails to distinguish tall, thin children from those who are short with adequate weight. Height-for-age is more useful for identifying children with short stature, a group often exposed to longer-term adverse conditions. Head circumference will be used through 24 months. Based on WHO norms, a measure of 2 standard deviations below the mean is chosen to indicate delay. Physical health indicators are recent diarrheal episodes and acute respiratory infections.

3.5 Similar Research

As mentioned above the relevance of the current project it is important to note that there is no published study evaluating the impact of a peer delivered perinatal depression intervention on child development outcomes. The project is also significant in its implications for public health: If the study

demonstrates a positive impact of the intervention on child outcomes, it will provide a major impetus to policy-makers and health-planners to address maternal depression in early child development strategies. The intervention, which is designed to be integrated into existing maternal and child health programs, and delivered by non-specialists, would provide a sustainable model for replication in other settings.

4. Dissemination and Utilization of Results

The research has the potential to make a major contribution to advancing our knowledge of the extent and manner by which an intervention to treat perinatal depression will improve outcomes for children. This study combines rigorous research designs built upon the extensive expertise of the investigators. By evaluating this type of task-shifting intervention in a South Asian setting with a high prevalence of perinatal depression, the knowledge gained could be instrumental in influencing the mental and maternal health policy agenda in the region.

5. Ethical Considerations

A support letter will be obtained from the Pakistan Ministry of Health. Ethical approvals will be obtained from the Duke Institutional Review Board (IRB). Written informed consent will be obtained from each participant before they participate. The participant will be given a written consent form prepared in Urdu. Any questions will be answered by the research team member conducting the interviews. If the participant agrees, she will sign the consent form. Participants may withdraw from the study at any time. Hard copy and electronic information will be kept confidential by storing the data in a locked file cabinet and on an encrypted/password protected devices, respectively. We will not share information with anyone outside of the project team.

Any study participant who needs specialist mental health care will be referred to centers; referral procedures are already in place through local partner institutions providing specialist mental health clinical care. Those needing general medical care will be referred to local health units and the concerned medical officer and community health worker will be informed by phone and/or a referral letter. Both control and intervention community health workers will be trained to recognize life-threatening or serious conditions and take appropriate action.

6. Annexes

Bachpan Trial Analysis Plan

Version 5.0

October 14, 2019

Contents

1	Purpose and scope.....	3
2	Description of the Trial	3
2.1	Principal research objectives and hypotheses to be addressed	3
2.1.1	Primary and secondary outcomes.....	4
2.2	Trial Design	4
2.3	Randomization	4
2.4	Sample size calculation.....	4
2.5	Intervention	5
2.6	Enhanced Usual Care (Control condition).....	6
2.7	Time of outcome assessment and visit windows	7
2.8	Data management	7
3	Data Analysis Plan.....	7
3.1	Analysis of primary and secondary outcomes	8
3.1.1	Analysis models and code.....	9
3.2	Sensitivity analyses	10
3.2.1	Moderator analyses.....	10
4	References.....	11
5	Tables and figures.....	13

1 Purpose and scope

This document provides the plan of analysis (statistical analysis plan) for the South Asian Hub for Advocacy, Research, and Education for mental health (SHARE) Child trial in Pakistan, conducted between October 2014 and August 2019. In Summer of 2018, the trial was renamed Bachpan. This plan covers the primary analysis comparing intervention arms and depressed and non-depressed perinatal women on their depressive symptoms at 36 months of age, in addition to comparing their children on various developmental outcomes at 36 months of age.

2 Description of the Trial

The Thinking Healthy Program (THP) is a community health worker (CHW)-delivered intervention which was developed in Pakistan and shown to have beneficial effects on both maternal depression and short-term child outcomes.

The current trial is described in detail in Turner et al.¹ In brief, the peer-delivered version of the THP was developed because of the lack of resources in many low and middle income (LMIC) countries to have professionals deliver the intervention. The present trial (THPP+) began in October 2014, and is an extension of the Thinking Healthy Program Peer-Delivered (THPP) trial, which is a six-month intervention delivered to women with perinatal depression, with the goal of reducing the burden of perinatal depression.² THPP+ is an extension of THPP in two ways: we follow the same sample of perinatally depressed women an additional 30 months; we recruited a sample of perinatally non-depressed women equal in sample size with the perinatally depressed group, and follow them for a total of 36 months, as well.

2.1 Principal research objectives and hypotheses to be addressed

The primary objective of the study is to evaluate the impact of a 36-month perinatal peer-delivered community-based perinatal depression intervention on (a) maternal depression and (b) child development. Our primary hypothesis for the perinatally depressed mothers is that the intervention will result in lower prevalence of depression at three years postnatal. Our primary hypothesis for the children is that the perinatal depression intervention will lead to improved developmental outcomes (see measures and constructs in Table 1) at three years of age. Additional child hypotheses address proposed mediators and moderators of the effects of the perinatal depression intervention on child outcomes; however, the mediators will be analyzed as part of a separate paper and so are not included in this document.

The second objective is to determine whether outcomes of perinatally depressed mothers and children in the intervention arm will converge to those in the reference group of perinatally non-depressed mothers and children as well as, secondarily, to determine whether there are any carryover effects of the intervention to benefit perinatally non-depressed mothers and children.

2.1.1 Primary and secondary outcomes

The primary and secondary outcomes are shown in Table 1. The primary mother outcome is Patient Health Questionnaire (PHQ-9). The primary child outcome is the Total Difficulties (TD) score from the Strengths and Difficulties Questionnaire (SDQ).

2.2 Trial Design

THPP+ is a stratified cluster randomized controlled trial, with 40 village clusters allocated in a 1:1 ratio to the intervention and control arms within 11 strata defined by Union Councils. The unit of randomization is a village cluster (a population of 2400–3600 with 2-3 adjacent catchment areas of LHWs). Participants are recruited from the community. The reason for choosing a village cluster as the unit of randomization is to minimize contamination between trial participants, since the delivery of the intervention is community based.

Approximately 14 women who screened depressed on the PHQ-9 (≥ 10) in each of the 40 village clusters were invited to participate in the trial. Bachpan also contains an embedded cohort of non-depressed women. In each of the 40 village clusters, an equal number of women who screened non-depressed on the PHQ-9 (i.e., approximately 14 per cluster) were invited to participate.

2.3 Randomization

Within each of the 11 union councils of the sub-district, village clusters were randomized to Intervention or Usual Care control using a 1:1 allocation ratio. Randomization was done before the participants were recruited. Research teams responsible for identifying, obtaining consent and recruiting trial participants were blind to the allocation status (to minimize the post-randomization recruitment bias). Randomization was stratified by union councils, to help minimize the imbalance between arms by factors likely to be associated with the primary outcome and reduce the between-cluster variability, hence increasing the power of the study. Allocation of clusters was carried out by an independent statistician based at the London School of Hygiene and Tropical Medicine (LSHTM) using a computerized randomization sequence.

The trial PI, site PIs/coordinators, trial statisticians and members of the Trial Steering Committee were blinded to the allocation status until the analysis of the six-month data for the parent trial, SHARE.

2.4 Sample size calculation

Much of the following is copied or adapted from the THPP+ protocol paper.¹

The primary power calculations for the THPP+ study are for the c-RCT comparisons of perinatally depressed women and their children in the control vs. intervention arms at 36 months postnatally at the 5% two-tailed significance level. As with the THPP trial,² we assume 40 village clusters randomized in a 1:1 allocation ratio within 11 union councils with 14 perinatally depressed women per village cluster to yield a total sample size of 560 perinatally depressed women at baseline. In addition, for THPP+, we recruit 14 perinatally non-depressed women per village cluster for a total of 560 perinatally non-depressed women at baseline. We conservatively estimate that loss to follow-up (including infant mortality and maternal illness and death) of both perinatally depressed and perinatally non-depressed women at 36 months will be 20%. Therefore, the total sample size available at 36 months is anticipated to be 480 perinatally depressed and 480 perinatally non-depressed women and their children. Using standard formulae^{3,4} for a cluster randomized design and assuming intra-cluster correlation of 0.07 in the intervention arm and 0.05 in the control arm, the trial will have 90% power at 36 months to detect a difference in perinatally depression remission of 65% in perinatally depressed-Intervention vs. 45% in perinatally depressed-control for the anticipated total sample size of 480 perinatally depressed women at 36 months. For child outcomes, this sample size will yield power of more than 90% to detect a difference between arms in mean total difficulties (TD) score (range 0-40) of 3 points for children of perinatally depressed mothers using plausible estimates for intra-cluster correlations of 0.04-0.08⁵ and 5.2 for standard deviation for the TD score among 3 year olds.⁶

Secondary comparisons mainly focus on child outcomes and are well powered. For the secondary hypothesis of equivalence between children of perinatally depressed mothers in the intervention arm and perinatally non-depressed mothers in the control arm, we will conclude equivalence if the 95% CI for the difference between the mean score in the two groups lies between -2 and 2 units. We note that differences of 1.0-2.0 points are often observed between boys and girls^{6,7}. With 220 children in each group and conservatively assuming an overall significance level of 2.5% (corresponding to the 95% CI), an SD of 5.2 and ICC of 0.04, and no difference between the groups, we will have 83% power to conclude equivalence.^{3,8} For the secondary research question of the community benefit (i.e. carryover) of the intervention for perinatally non-depressed women and their children, we will have 80% power to detect a 1.7 or greater impact of the intervention on mean TD score (Groups perinatally non-depressed-Intervention vs. perinatally non-depressed-Control, Figure 1) for the same assumptions of the primary comparison above.

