2.8 Data management

Baseline and follow-up outcome data is captured electronically using tablet computers. In addition, process data from peers is also collected. Baseline and outcome data is remotely uploaded as a CSV (comma-separated values) file to the main data server, which run on the software program ODK. Both files are compliant with good clinical practices (including a date and time stamp of original data entry and with an audit trail to document any subsequent changes). Process data is to be collected in paper form, and this is to be manually entered and stored as CSV files using the same data collection platform. THPP quality-related data is also be collected in paper form.

All data, range and consistency checks are performed at weekly intervals separately for each data source. Any queries identified are resolved promptly by the data management team, and the database is updated, maintaining the audit trail. Consistency checks are performed using PostgreSQL, pgAdminIII (ie SQL based queries run on the server). This includes Trial I.D duplication/mismatch, merging two tables in case any changes are made in the questionnaire.

Additional data quality checks are performed by a biostatistician at Duke University.

3 Data Analysis Plan

The main trial paper for both moms and children will focus on the 36-month outcomes solely. Statistical analysis will be conducted according to the CONSORT guidelines.^{11,12} A flow chart will show participation of both perinatally depressed (by intervention arm) and perinatally non-depressed

mothers and their children from recruitment in the third trimester through to 36 months postnatally (Figure 2 is an example, but in practice it will be more detailed). Withdrawals and loss to follow-up will be shown at 36-month post-intervention. All analyses will focus on comparison of three groups: perinataly depressed intervention, perinataly depressed control, and perinataly non-depressed, although we will test for a differential effect by non-depressed in intervention vs. control as a supplemental analysis.

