Baseline characteristics of recruited mothers will be reported by study arm for perinataly depressed women, and overall for perinataly non-depressed women. Continuous variables will be summarized by means and standard deviation (SD), or medians and the 25th and 75th percentile, if needed. Categorical variables will be summarized by counts and percentages. Distributions of outcomes will also be explored using graphical techniques such as box plots and histograms.

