BSITD-III	An individually administered assessment of the child’s achievement of developmental milestones across two areas: fine motor and receptive language. ²⁵	The total score from each domain, rescaled using the provided age-scaled score.	The standard scores are derived from the U.S. norms; and, because there are no available Pakistani norms, the scores provide a metric with which to compare groups of children in this Pakistan setting relative to the study hypotheses.
SCID	Structured clinical interview for depression. ²⁶	Prevalence of depression	
Other Outcomes			
Recurrence	Only measured in prenatally depressed. This measures in those who recovered by 6 months (based on SCID), how many had a recurrence of depression (based on SCID) by 36 months?		
SCID across time	Prevalence of depression from baseline through 36 months, all fit in one longitudinal model.		
Child Anthropometrics	Weight-for-age and height-for-age z-scores, based on WHO criteria		

Table 2. Moderators

Measure	Description
Socio-economic status (SES)	Asset-based SES index (dichotomized at the bottom 1/3 of the distribution) Maternal education (dichotomized at no education)
Household composition	Nuclear family status (nuclear vs. non-nuclear)
Intimate partner violence (IPV)	Any type of IPV in the past 12 months
Child Gender	
Treatment Expectations	Very/moderately useful vs. somewhat/not useful
Maternal age	18-24 vs. 25+
Depression severity	PHQ-9 = 10-14 vs. 15+
Depression chronicity	<12 weeks vs. ≥12 weeks
Parity*	<4 kids vs. 4+ kids

* Only considered a moderator for maternal outcomes

[figure not shown]

Figure 1.

[figure not shown]

Figure 2.

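### The SAP plans no between-arm count of maternal or child deaths, least of all among non-depressed women

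*SAP*

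**What the plan says.** - **Loss allowance (SAP 2.4).** The sample size assumes: "loss to follow-up (including infant mortality and maternal illness and death) of both perinatally depressed and perinatally non-depressed women at 36 months will be 20" per cent. No separate rate is given for any of these events.
- **Flow chart (SAP section 3).** Depressed women are followed by arm; for non-depressed women no arm is named. "Withdrawals and loss to follow-up will be shown at 36-month post-intervention", with no breakdown by cause specified. The section commits to CONSORT and calls Figure 2 an example that will become more detailed.
- **Baseline table (SAP section 3).** Characteristics are "reported by study arm for perinataly depressed women, and overall for perinataly non-depressed women".
- **Missing outcomes (SAP 3.1).** The primary analysis uses complete cases, adjusted for covariates found imbalanced at baseline or by loss to follow-up. Pattern-mixture analyses follow only if there is concern that data are missing not at random. Death is not mentioned.
- **Outcomes (SAP Table 1).** PHQ-9, SDQ-TD, WHO-DAS, Bayley, SCID, recurrence and growth are listed. There is no death or adverse-event outcome, and the SAP has no safety section.
- **Non-depressed women by arm.** SAP 2.1 makes carryover benefit a secondary question, SAP 2.4 gives power for it, and SAP section 3 tests it as a supplemental analysis. Protocol 3.1 expects these women to benefit from the community component.

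**The concern.** Nothing later in the SAP separates again the events that section 2.4 merges into loss. A mother who dies has no 36-month PHQ-9, and a child who dies has no 36-month SDQ-TD. Both leave the models in the same way as a family that moved away. Equal total losses in two arms could therefore conceal unequal deaths.

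The gap is widest for non-depressed women. They form a randomised comparison (intervention against control clusters) with its own power statement, yet neither their losses nor their baseline characteristics are planned by arm. A reader of the supplemental test would have no by-arm attrition or mortality to set beside it.

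At stake is whether a three-year trial starting in pregnancy reports deaths by randomised arm. A secondary matter is that the remission estimate is conditional on survival without saying so.

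**Working it through.** **1. The plan's own loss figure.** Inputs: "total sample size of 560 perinatally depressed women at baseline", the same number of non-depressed women, and 20% loss (SAP 2.4).

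- 560 x 0.80 = 448 per depression group. The SAP states 480, which is a loss of 80/560 = 14.3%.
- Total losses: 0.20 x 1,120 = 224 by the stated rate, but 1,120 - (480 + 480) = 160 by the stated sample.
- Protocol 3.1 expects 220 of 280 to complete in each of four groups: 4 x 60 = 240 losses (21.4%).

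So the planned losses are 160, 224 or 240, depending on the sentence used. The stated 90% remission power survives either way (92.0-93.8% at 480; 91.0-92.9% at 448, depending on the formula). The discrepancy matters here only as a denominator.

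**2. Where a death would surface if the SAP is followed as written.**

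| Group | Flow chart | Baseline table | Outcome models |
|---|---|---|---|
| Depressed, intervention | in total losses, by arm | by arm | absent (complete case) |
| Depressed, control | in total losses, by arm | by arm | absent |
| Non-depressed, intervention | in total losses, no arm stated | pooled | absent |
| Non-depressed, control | in total losses, no arm stated | pooled | absent |

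SAP 2.4 also counts infant death as loss of the woman. The SAP does not say whether a mother whose infant died is still assessed.

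**3. How much of the loss could be death.** No rate is given. Assume child mortality of 3%, 5% or 8% to 36 months.

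| Assumed risk | Deaths in 1,120 | Per group of 280 | Share of 224 | Share of 160 |
|---|---|---|---|---|
| 3% | 33.6 | 8.4 | 15% | 21% |
| 5% | 56 | 14 | 25% | 35% |
| 8% | 89.6 | 22.4 | 40% | 56% |

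**4. What a by-arm comparison could show.** Design: "40 village clusters randomized in a 1:1 allocation ratio within 11 union councils with 14 perinatally depressed women per village cluster", so 280 per arm, or 560 per arm with non-depressed women added. At an assumed 5% risk the 95% CI half-width is 1.96 x sqrt(2 x 0.05 x 0.95 / n):

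- n = 560: 2.55 points; with an assumed design effect of 1.3, 2.55 x sqrt(1.3) = 2.91.
- n = 280: 3.61 points; with the same design effect, 4.12.

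Power to detect a doubling, two-sided 5%, uses effective n = n / (1 + (m - 1) x ICC), with m = 14 or 28 and an assumed ICC from 0.02 down to 0:

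| Assumed control risk | 280 per arm | 560 per arm |
|---|---|---|
| 2% | 23.4-28.3% | 35.2-50.1% |
| 4% | 42.7-51.3% | 62.3-80.6% |
| 8% | 73.9-83.2% | 91.5-98.5% |

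**5. Effect on remission.** Take 65% against 45% (SAP 2.4) as remission among survivors. The complete-case difference is 20.0 points whatever the mortality. Counting maternal death as not remitted, under assumed death rates:

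- 2% against 0%: 0.98 x 65 = 63.7; 63.7 - 45.0 = 18.7 points.
- 4% against 2%: 0.96 x 65 - 0.98 x 45 = 62.4 - 44.1 = 18.3 points.
- 8% against 4%, a deliberately extreme case: 0.92 x 65 - 0.96 x 45 = 59.8 - 43.2 = 16.6 points.

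**The case against.** The sentence in SAP 2.4 is an attrition allowance, not an analysis rule, and does not say how deaths will be reported. That is right: the removal of deaths from the models follows from the complete-case text in SAP 3.1.

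A reader might go on to infer that the plan could not show any harm of the intervention. The documents do not support that. The primary comparison is powered "at the 5% two-tailed significance level", and the arms are compared on maternal and child scales and growth, any of which could show worsening. These analyses are nevertheless limited to dyads with a 36-month outcome, so they cannot show excess deaths.

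A reader might also infer that non-depressed women are never examined by arm. SAP section 3 does plan that test. What is missing is the by-arm flow and baseline data behind it.

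Nor should the allowance be read as covering only serious illness; the SAP says illness, undefined. Partner violence and child illness are a further temptation. The first enters the SAP as a moderator, "Any type of IPV in the past 12 months". Of the second, Protocol 3.3 says: "Physical health indicators are recent diarrheal episodes and acute respiratory infections". Neither document calls them harm outcomes, and making them so would be a reviewer's preference.

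Two points limit the finding. The flow chart is to follow CONSORT and be more detailed than Figure 2, which is not visible in the text reviewed, so causes of loss may appear in practice. A safety procedure may also exist in the protocol paper that the SAP cites, or in the part of the protocol removed before review. The judgement concerns the SAP as written. Finally, power for deaths is low at low risks, which is a reason to report estimates without a formal test, not a reason to omit the counts.

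**Conclusion.** The concern holds in a limited form. Followed as written, the SAP merges infant death, maternal illness and maternal death into loss to follow-up, has no rule for death in the analysis, and plans no by-arm mortality. For non-depressed women it plans no by-arm losses at all, although it compares their outcomes by arm.

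The size is uncertain because the documents give no death rate. The 15-40% share of 224 losses (21-56% of 160) rests wholly on an assumed child mortality of 3% to 8%. The effect on remission is small at low maternal mortality: about 1.3 points for an assumed 2% in the intervention arm and none in control, against a planned 20. This is therefore a cheap improvement in reporting and does not threaten the primary conclusion.

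**What to change.** In SAP section 3:

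1. Show the flow chart and baseline table for all four groups: depressed and non-depressed, each by intervention and control.
2. Tabulate maternal death and infant or child death separately from withdrawal and untraced, in the same four groups, with all enrolled dyads as the denominator. State how dyads excluded after birth under Protocol 3.1 are counted. Give a descriptive cluster-adjusted difference with 95% CI by randomised arm; a comparison of cluster-level proportions would do. Maternal illness can stay as a listed reason for loss, since the SAP does not define it.
3. Add one sensitivity analysis of remission in which maternal death counts as not remitted.
4. Reconcile the 20% loss with the stated 480 + 480.

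The cost is a few lines of SAP text, one table and one extra model. The reasons for loss should largely be to hand for the CONSORT flow chart. The downside is small counts and wide intervals, so the death comparison should be labelled descriptive.

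### SAP 2.4 expects 480 women per depression group at 36 months, but 20% loss from 560 leaves 448; the 80% carryover power holds only in the lower part of its stated ICC range

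*SAP*

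**What the plan says.** Section 2.4 of the SAP takes 40 village clusters with 14 perinatally depressed women each "to yield a total sample size of 560 perinatally depressed women at baseline", and the same number of non-depressed women. Its loss assumption, which covers both groups, reads "perinatally non-depressed women at 36 months will be 20" per cent. From this it concludes that "the total sample size available at 36 months is anticipated to be 480 perinatally depressed and 480 perinatally non-depressed women and their children". The remission power is then stated "for the anticipated total sample size of 480 perinatally depressed women at 36 months", and the power for a 3-point TD difference uses the same sample, with SD 5.2 and ICCs of 0.04-0.08.

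The next paragraph opens with "Secondary comparisons mainly focus on child outcomes and are well powered". The equivalence calculation there begins "With 220 children in each group" and names an ICC of 0.04. For the carryover question (non-depressed intervention against non-depressed control) it says "we will have 80% power to detect a 1.7 or greater impact of the intervention on mean TD score" and adds "for the same assumptions of the primary comparison above", with no ICC of its own. Protocol section 3.1 expects 220 of 280 dyads per arm to complete.

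**The concern.** The 480 is presented as the result of applying the loss rate to the baseline number, and it is not that result. It is also the named input to the primary power statement, while the next paragraph works from a smaller sample. A reader comparing the achieved 36-month count with the plan could use 480, 448 or 440.

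The carryover claim borrows a range of ICCs from the primary comparison but gives a single power. If 80% is not reached over that range, a null carryover result would be read against more power than the plan's own assumptions support.

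**Working it through.** **Retention**

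- Stated inputs (SAP 2.4): 560 per depression group, 20% loss. 560 × 0.80 = 448, i.e. 224 per arm and 11.2 per cluster.
- Attempts to recover 480: 480/560 = 0.857, a 14.3% loss; 480/0.80 = 600, a baseline that appears nowhere; 560/1.2 = 467; 480 × 1.2 = 576. None links 560 and 480 at 20%.
- 220 per arm: 440/560 = 0.786, a 21.4% loss.
- Gap between stated and derived: 480 − 448 = 32 women per depression group.

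**Formulas**

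Take 20 clusters per arm, n per arm, m = n/20 per cluster and a two-sided 5% test. In each range below, the lower figure uses a noncentral t with 38 df and the higher one the normal approximation.

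- TD score: SE = 5.2 × √[2(1 + (m − 1) × ICC)/n].
- Remission: variance = [0.65 × 0.35 × (1 + (m − 1) × 0.07) + 0.45 × 0.55 × (1 + (m − 1) × 0.05)]/n.

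**Primary claims**

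Remission at n = 240, m = 12: variance = (0.2275 × 1.77 + 0.2475 × 1.55)/240 = 0.003276, SE = 0.0572, and 0.20/0.0572 − 1.96 = 1.53, giving 93.8% (92.6% with t). The claim of 90% is met. At 448 power is 91.6-92.9% and at 440 it is 91.3-92.6%. Power for 3 TD points is above 99% at all three samples and at every ICC from 0.04 to 0.08.

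**Equivalence**

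At n = 220, m = 11, ICC 0.04: SE = 5.2 × √(2 × 1.40/220) = 0.587. The probability that the 95% CI lies within ±2, given no true difference, is 83-85%. The stated 83% therefore reproduces from 220; 240 per group would give 85-88%.

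**Carryover, 1.7 points**

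Example at n = 240, m = 12, ICC 0.08: SE = 5.2 × √(2 × 1.88/240) = 0.651, and 1.7/0.651 − 1.96 = 0.65, giving 74.3% (72.1% with t).

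| n per arm | ICC 0.04 | ICC 0.06 | ICC 0.08 | Highest ICC with 80% power |
|---|---|---|---|---|
| 240 | 83-85% | 77-79% | 72-74% | 0.050-0.058 |
| 224 | 81-83% | 76-78% | 71-73% | 0.044-0.052 |
| 220 | 81-83% | 75-77% | 70-72% | 0.042-0.050 |

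At ICC 0.08 the difference detectable with 80% power is 1.82-1.87 points at 240 per arm and 1.86-1.90 at 224, against the stated 1.7.

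**The case against.** Nothing can be said for deriving 480 from 560 at 20% loss. The stronger defence concerns the rest.

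- **The 80% reproduces at inputs printed in 2.4.** With 240 per arm and ICC 0.06, the midpoint of the range, the normal approximation gives 79.4%. With 220 per arm and ICC 0.04, the inputs of the preceding equivalence sentence, and one cluster per arm deducted, it gives 80.6% and a detectable difference of 1.69. The fault may then be a loose cross-reference. This stands as a possible origin of the number, but each match needs a single ICC that the SAP does not attach to carryover. Read plainly, the sentence refers to the primary TD assumptions, and those are a range.
- **220 may be 224 rounded down.** That is plausible, since 280 × 0.80 = 224 and the protocol states no loss percentage. It makes 220 a small departure, but 2.4 still uses 240 per arm in one paragraph and 220 in the next.
- **Retention can be judged against the 20% rate directly.** True for the rate. It does not help anyone comparing counts.
- **The practical effect is small.** This stands. SAP section 3 makes carryover a supplemental analysis, and the SAP is dated October 2019, after conduct ended in August 2019.

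A one-sided 5% test would keep carryover power above 80% throughout under the normal approximation, but 2.4 specifies two-tailed.

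**Conclusion.** The concern holds and is minor. The stated 36-month sample is wrong as written: if the 20% loss is the intended assumption, 480 overstates it by 32 women per depression group. The 80% carryover power is not true over the ICC range it is tied to: at the SAP's own 480 it falls to 72-74% at the upper end, and at 448 to 71-73%. No primary conclusion changes, and the 83% equivalence figure is correct at its disclosed inputs. No enrolment decision depends on any of this.

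The power figures assume equal cluster sizes, 20 clusters per arm, SD 5.2 and no precision gain from stratum or covariate adjustment. Such adjustment could raise power, but the SAP gives no figure for it.

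**What to change.** 1. Choose one 36-month sample and use it in every calculation in 2.4: 448 per depression group (224 per arm) if the 20% loss stands. Otherwise restate the loss as about 14% for 480 or about 21% for 440.
2. For carryover, either state the ICC behind the 80%, or restate the power at 224 per arm as about 81-83% at ICC 0.04, 76-78% at 0.06 and 71-73% at 0.08.
3. Qualify the general statement about the power of the secondary comparisons as applying at ICCs near 0.04-0.05.
4. Leave the 83% equivalence figure as it is, with its ICC of 0.04 shown.

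The cost is wording only. The planned sample (if the 20% stands) and the carryover power look slightly less favourable; the remission, TD and equivalence claims stand.
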